## MANAGEMENT OF RISKS TO SUBJECTS

### Expected AEs

Expected AEs associated with the exercise intervention include:

- Fatigue
- Muscle Soreness
- Mild Shortness of Breath
- Mild Tachycardia
- Transient increase in blood pressure
- Lightheadedness
- Excessive Sweating
- Muscle strain or sprain

### AE Management

Participants experiencing a mild AE (e.g. fatigue or muscle soreness) related to the intervention will have discretion as to whether they want to continue with the intervention exercise regimen. They will be

advised to rest if they want to stop during an intervention session or want to skip a session due to mild AE.

Mild lightheadedness will be treated with slightly more caution than other mild AEs. Participants will be instructed that if during exercise, they experience lightheadedness they should immediately discontinue the exercise. If the lightheadedness persists after discontinuation, they will be instructed to consult a medical professional. If the lightheadedness resolves, the participant can resume normal activities, including the exercise regimen.

If a participant experiences a moderate or severe AE, they will be instructed to cease the exercise regimen for recovery, if necessary, and the PI and co-investigators will evaluate whether re-entry to the exercise regimen is acceptable.

If a participant experiences an SAE, they will be instructed to cease the exercise regimen.

## **DATA ANALYSIS PLANS**

[figure not shown]
As this is a pilot study, there will be insufficient numbers to conduct a well-powered interim analysis. The study team will examine SAEs and expected AEs in aggregate at the midpoint of the study to examine whether disproportionate SAEs or AEs have occurred in the intervention participants. While there is unlikely to be statistical power in interim analysis, we will conduct bi-variate statistical analysis consisting of chi-square tests to evaluate the proportion of SAEs and AEs in intervention participants versus control participants. The investigators will review this statistical analysis. Discussions of whether sufficient evidence exists for stopping the trial early will involve consideration of whether the AEs are related or unrelated to the study activities.

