## 4.0 STUDY DESIGN

### 4.1 Description of Study

This is a pilot study of a 2-arm randomized trial with a 2:1 initial allocation to exercise intervention or waitlist control (see Appendix B for study schema). The intervention group will then be randomly assigned (1:1) to receive either a 12-week aerobic exercise (AE) intervention or a 12-week resistance exercise (RE) intervention.

At 12 weeks, the intervention group will be assessed for intervention response, defined as a  $\geq 5\%$  increase in 6-minute walk distance (6MWD) over baseline. Non-responders to either AE or RE will receive 12 weeks of combined AE+RE. Intervention responders will continue the exercise intervention in their current assignment, either AE or RE alone, for the additional 12 weeks.

This study will employ a waitlist control. After 24 weeks, the waitlist control group will receive a digital copy of sessions provided to the intervention arm. The control and intervention arms' schedule of evaluations will be identical across all 24 weeks of the trial.

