#### 4.3 Study Procedures

#### 4.3.1 Recruitment

This project will recruit 30 study participants through a multi-pronged approach:

Seattle Cancer Care Alliance (SCCA) clinics: At SCCA, we will work with the breast oncology clinic research team to obtain a list of potentially eligible research participants that will include patient name, phone number, and mailing address. This eligibility will be based on age and approximate end date of chemotherapy or Herceptin therapy. Potentially eligible participants identified through SCCA will receive a mailed letter endorsed by their oncologist inviting them to call the study coordinator for more information and/or screening. The study team may follow up proactively with a phone call no less than two weeks after sending the letter.

Breast cancer support groups in the community: Study information will be provided to breast cancer support groups in the community by sharing study flyers (paper, electronic, or Web versions) with the organizers of these groups and by giving presentations at in-person group events, as permitted by organizers.

Re-contacting previous breast cancer research participants: The pool of previous breast cancer research participants will be generated from past projects under the purview of the study's principal investigators or shared from affiliate investigators. Previous participants or candidates will be contacted via phone, email, or mailed letter, depending on what information is available to the study PIs.

The UW ITHS Leaf tool: The University of Washington's Leaf system will be used to generate an identifiable cohort of potentially eligible patients in the UW Medicine system. The study will query the database for patients who meet key eligibility criteria and who have recently visited the UW Medicine system for treatment. Candidates generated from this list will be sent a letter that describes the study and invites them to contact the study team should they be interested in participation. The study team may follow up proactively with a phone call no less than two weeks after sending the letter.

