#### 4.3.4 Randomization

Participants will be randomly allocated to the intervention or waitlist control arm using blocked randomization (2:1 intervention to control), stratified upon whether the participant has received “AC” chemotherapy (doxorubicin and cyclophosphamide combination therapy). Intervention participants will then be randomized to either aerobic exercise training or resistance strength training, again using blocked randomization stratified on AC treatment history. Randomization will be performed in REDCap with the REDCap Randomization module.

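### The midpoint safety look uses chi-square tests on arms too small for the approximation, with the sample and the counting unit undefined

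*Combined protocol and SAP*

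**What the plan says.** Under Data Analysis Plans in Appendix A, the study team will look at serious and expected adverse events "at the midpoint of the study to examine whether disproportionate SAEs or AEs have occurred in the intervention participants". The method is given as: "we will conduct bi-variate statistical analysis consisting of chi-square tests to evaluate the proportion of SAEs and AEs in intervention participants versus control participants". The same paragraph adds "The investigators will review this statistical analysis", and any decision to stop early is a discussion that weighs whether events are related to study activities.

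The paragraph gives no significance level, continuity correction, exact alternative, boundary or definition of the midpoint. It does concede low power, in the words "While there is unlikely to be statistical power in interim analysis" and in its opening sentence.

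The size follows from Section 4.3.1 ("This project will recruit 30 study participants through a multi-pronged approach") and Section 4.1 ("2-arm randomized trial with a 2:1 initial allocation to exercise intervention or waitlist control"). Section 10.0, for the final safety analysis, counts adverse events rather than women.

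**The concern.** The aim is to detect an excess of harm in exercisers. A chi-square test relies on a large-sample approximation, and one arm here may hold five women. When arms are unequal and events uncommon, the failure is lopsided: a couple of events in the small arm can cross the threshold, while a larger number in the big arm does not. That is the opposite of what the look is for.

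The unit is also unsettled. The sentence can be read as the proportion of women with an event or as a share of events. Appendix A lists soreness and fatigue among the expected events, and these can recur in the same woman. A chi-square on event totals treats each recurrence as independent.

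At stake is what the investigators take from the result when they discuss whether the trial should go on.

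**Working it through.** The plan states no power, error rate or event rate for this look, so there is no figure of its own to reproduce.

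**Inputs.** N = 30 (Section 4.3.1); 2:1 allocation (Sections 4.1 and 4.3.4). The midpoint is undefined, so two cases are used: half enrolled, 10 vs 5; all enrolled, 20 vs 10. Assumed, because not stated: two-sided 0.05, no continuity correction, and the event risks shown.

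**1. Expected counts.** With t women having an event, n exercisers and m controls, the smallest expected count is m × min(t, N − t)/N.
- 10 vs 5: largest possible value 5 × 7/15 = 2.3.
- 20 vs 10: largest possible value 10 × 15/30 = 5, reached only at t = 15.

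The usual condition of at least 5 in every cell is never met in the first case and is met at a single total in the second.

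**2. Individual tables.** With a events among n and b among m, X² = N[a(m − b) − b(n − a)]² / [n m t (N − t)].
- 0/10 vs 2/5: 15 × 20²/(10 × 5 × 2 × 13) = 4.62, p = 0.032. Yates 0.18. Fisher C(5,2)/C(15,2) = 10/105 = 0.095.
- 5/10 vs 0/5: 15 × 25²/(10 × 5 × 5 × 10) = 3.75, p = 0.053.
- 6/10 vs 0/5: X² = 5.00, p = 0.025.
- 0/20 vs 2/10: 30 × 40²/(20 × 10 × 2 × 28) = 4.29, p = 0.038. Yates 0.20, Fisher 0.10.
- 6/20 vs 0/10: 30 × 60²/(20 × 10 × 6 × 24) = 3.75, p = 0.053.

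Two control events against none are flagged. Five exerciser events against none (six at 20 vs 10) are not.

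**3. False flags by direction.** Binomial probabilities summed over all tables with p < 0.05, with the same true risk in both arms:

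| Arms | Common risk | Control excess | Intervention excess |
|---|---|---|---|
| 10 vs 5 | 10% | 3.2% | 0.01% |
| 10 vs 5 | 20% | 4.6% | 0.2% |
| 20 vs 10 | 10% | 3.6% | 0.08% |
| 20 vs 10 | 20% | 2.7% | 1.0% |

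The two directions balance at a common risk of 50% and swap above it, so the lopsidedness described here belongs to uncommon events. Over all common risks, the two directions together never exceed 5.0% at 10 vs 5 or 5.2% at 20 vs 10.

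**4. Power toward harm** (intervention vs control risk; Pearson in the harm direction, then one-sided Fisher at 0.05):

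| Risks | 10 vs 5: Pearson | 10 vs 5: Fisher | 20 vs 10: Pearson |
|---|---|---|---|
| 30% vs 10% | 2.8% | 2.8% | 15.6% |
| 50% vs 20% | 14.8% | 14.6% | 35% |
| 80% vs 20% | 68% | 62% | 93% |

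For one-sided Fisher, 5/10 vs 0/5 gives C(10,5)/C(15,5) = 252/3003 = 0.084, and 6/10 vs 0/5 gives C(10,6)/C(15,6) = 210/5005 = 0.042. The harm threshold with no control events is therefore 6/10 under either test.

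**5. If events are counted.** Event totals at 10 vs 5 were simulated with equal true rates and tested by chi-square against the 2:1 expectation. With independent (Poisson) events the rejection rate is about 5%. With assumed clustering (mean 1 to 4 events per woman, negative-binomial k from 2 down to 1) it runs from about 10% to about 37%.

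**The case against.** The strongest reply is that the plan already says the look cannot be powered, and that insensitivity comes from the sample, not from the test. That stands. The power table shows that Fisher's test does no better, and at a one-sided 0.025 it would need 7/10 vs 0/5. A reader might infer that an exact test would let the look detect harm. It would not.

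Other replies also limit the point:
- 10 vs 5 is one reading of an undefined midpoint. At 20 vs 10 and 20% risk the imbalance is milder.
- The control-excess flag needs the uncorrected test. Yates removes it, but the plan names no correction, and Yates also moves 6/10 vs 0/5 to p = 0.094.
- A reader might infer that the test rejects too often in general. At participant level it does not, and the event-level inflation requires both event counting and clustering. The phrase about intervention versus control participants favours a participant-level reading without settling it.
- A reader might infer that the trial could be stopped on this p-value, or that nothing else protects participants. No boundary is tied to it. Section 8.0 and Appendix A provide real-time review of serious events and monthly and quarterly reviews.
- The look is not blind to very large differences in common events, as the 80% vs 20% row shows.

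What the disclosure of low power does not cover is an approximation outside its range, the direction in which it errs for uncommon events, and the undefined unit and timing.

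**Conclusion.** The point holds as a defect of method and specification. The expected-count failure depends only on the sample size and allocation. The directional figures rest on an uncorrected Pearson test, two-sided 0.05 and a common event risk below one half; the 4.6% vs 0.2% contrast also assumes half enrolment. The 10% to 37% event-level range is conditional on assumed clustering.

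The documents do not support a claim of hidden low power, of general type I inflation, or of a stopping decision resting on this test. The change should be made because a better method costs almost nothing and can change what the investigators see: 0/10 vs 2/5 would no longer appear as a significant difference.

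**What to change.** In Data Analysis Plans, Appendix A, replace the chi-square tests with the following:

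1. For each arm, give the number of participants with at least one serious adverse event, and with at least one adverse event, over participants randomised, with exact 95% confidence intervals per arm and for the risk difference.
2. If a p-value is wanted, use Fisher's exact test in the direction of intervention excess, with its level stated.
3. Report event counts descriptively, without a test.
4. Define the midpoint, for example by number enrolled or by follow-up completed.
5. State that a non-significant result is not evidence of safety.

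The intervals make the last item concrete: 0/10 has an exact two-sided 95% upper limit of 1 − 0.025^(1/10) = 31%, and 0/20 one of 17%.

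The cost is a few sentences and trivial programming. P-values become slightly more conservative, and sensitivity to harm stays low. The change also does not address the extra chance of detecting events during supervised sessions, which only the intervention arm attends, so the report should note it beside the counts.

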## **PLAN FOR DATA MANAGEMENT**

Compliance of regulatory documents and study data accuracy and completeness will be maintained through an internal study team quality assurance process.

Confidentiality throughout the trial is maintained by recording all study data on paper or computerized forms with no personal identifying information. A 3-digit number will be assigned to each subject. Only the PI and the HIPAA-trained study coordinator will have access to the file that links names with subject study identifiers. To ensure confidentiality, no personal identifying information will be coded on the questionnaires or sample data. A separate document will contain contact information but will not contain personal data or protected health information that is collected as part of the study. Study data will be stored in a REDCap database that only the PI and the study coordinator can access. All paper data, including consent forms, will be stored in locked file cabinets in a locked office and on password-protected computers located behind a secure firewall.

## Appendix B – STUDY SCHEMA

## Appendix C – MRI PROTOCOL

### General Overview

This appendix details the abdominal imaging (ABD\_LOC and ABD\_FAT) and thigh skeletal muscle imaging (3Plane\_LOC\_Thigh and T1 AX DB Left Thigh\_TE36) for participants in the “Investigating Various Adaptive-Training Exercise Programs for Improving Cardiorespiratory Fitness After Breast Cancer Treatment” (ACTIVATE) study. This is a 30-min MR exam. Contact the study team for any clarification on this exam. Different sections of this protocol are as follows:

### MRI Protocol– List of Sequences

Body Composition with localizers
ABD LOC
T1 AX ABDOMEN FAT (L2-L4)
3Plane_LOC_thigh
T1 AX DB Left thigh_TE36

**\*Please place the following information in the Patient Registration Window before the exam begins:**

- Place with the study ID number in the MRN Field.
- Place the acrostic in the Patient Name Field.
- These should be given to you by the Study Coordinator.

**Series Name:** ABD\_LOC (REF A)

**Series Description:** Abdominal Localizer

**Notes:** Perform multi-plane abdominal localizer (coronal and sagittal). A sagittal plan that appreciates L2-L4 will be used in planning future series.

### Series Prescription Details

	Series Rx Notes
Prescribe series from:	Localize the lumbar region
Orientation:	Coronal and Sagittal
Number of Slices	3-5 sagittal slices; 8-10 coronal slices
Breath-holding:	Yes

### Image Parameters

Image Parameter	Value
Slice Thickness	5mm
Slice Gap	5 mm
TR	260
TE	1.08
Number of Phase Encodings	143
Percent Sampling	75 %
Percent Phase FOV	100%
Pixel Bandwidth	1132
Matrix	192 x 144
Flip Angle	65 degrees

### Sample Images

[figure not shown]
**Series Name:** ABD\_FAT (REF B)

**Series Description:** T1 weighted turbo spin-echo sequence acquired with 3 evenly spaced axial slices with 1st and 3rd centered at L2 and L4.

**Notes:** To assess visceral fat, a series of images will be acquired to assess visceral fat volume. Open up field of view (FOV) to encompass all of the abdomen.

#### Series Prescription Details

	Series Rx Notes
Prescribe series from:	ABD_LOC (Ref A)
Orientation:	Axial
Number of Slices	3 evenly spaced axial slices with 1 st and 3 rd centered at L2 and L4.
Breath-holding:	Yes, breath hold per slice

### **Image Parameters**

Image Parameter	Value
FOV	Open to encompass all of the abdomen
Slice Thickness	5mm
Slice Gap	Variable – change distance factor as necessary
TR	800 ms
TE	36 ms
Flip Angle	180 degrees
Matrix	256 * 256
Acceleration factor	2
Bandwidth	305 Hz/Px
Turbo factor	11
Echo trains per slice	13
Gating	ECG triggering

### **Sample Image(s)**

**Series Name:** 3Plane\_LOC\_Thigh (REF C)

**Series Description:** Thigh Localizer

**Notes:** Perform multi-plane localizer on thigh with additional body matrix coil.

### **Series Prescription Details**

	Series Rx Notes
Prescribe series from:	3PLANE Loc thigh
Orientation:	Coronal, Sagittal, Axial
Number of Slices	3-5 per orientation
Breath-holding:	No

### **Image Parameters**

Image Parameter	Value
Slice Thickness	5mm
Slice Gap	5 mm
TR	260
TE	1.08
Number of Phase Encodings	143
Percent Sampling	75 %
Percent Phase FOV	100%
Pixel Bandwidth	1132
Matrix	192 x 144
Flip Angle	65 degrees

**Series Name:** **T1 AX DB Left Thigh\_TE36 (REF D)**

**Series Description:** T1 weighted turbo spin-echo sequence acquired with 5 evenly spaced axial slices. The position of center slice will be determined by distance measured by study staff.

**Notes:** A series of images will be acquired to assess muscle and fat composition of left thigh.

**Formula for slice location:**

- \* Patient's height in inches x 0.125 = distance from distal femur
- \* Inches x 25.4 = mm
- \* Start at distal femur (condyle) and measure up "X" amount of mm to get location for center slice
- \* Use left leg
- \* Example: Pt Height = 64.3 inches x 0.125 x 25.4 = 204 mm

**Series Prescription Details**

	Series Rx Notes
Prescribe series from:	3PLANE_Loc_thigh
Orientation:	Axial
Number of Slices	5
Breath-holding:	No

**Image Parameters**

Image Parameter	Value
Slice Thickness	5mm
Slice Gap	1 mm
TE	36
FOV	256 x 256 mm 
Base resolution	384 x 384 pixels
In plane resolution	0.7 x 0.5

**Sample Image(s)**

## MRI Encounter Guide

REF	Series Name	Acq time (~sec)	Series Description / Notes	Series #
A	ABD_LOC	9	Sagittal localizer for L2-L4	
B	ABD_FAT	3x10	3 evenly spaced axial slices with 1 st and 3 rd slice centered at L2 and L4	
C	3Plane_LOC_Thigh	15	Multi slice localizer of thigh	
D	T1 AX DB Left Thigh_TE36	20	Use formula for REF D to plan slice	

**The MRI Encounter Form must be completed for each MRI exam. Please use this document as a guide to completing the MRI exam and MRI Encounter Form.**

## APPENDIX D – Intervention Protocol

### Exercise Intervention Overview

Exercise Type	Aerobic	Strength	Combined
Mode	Walking (with guided in-home sessions provided 1 time/week)	Resistance activity (with guided in-home sessions provided 1 time/week)	Both aerobic and resistance activities, starting each session with aerobic activities
Frequency	3 times/week	Level 1: 2 times/week Levels 2 & 3: 3 times per week as tolerated	3 times/week
Time	Level 1: 90 min/week (30 min sessions) Level 2: 120 min/week (40 min sessions) Level 3: 150 min/week (50 min sessions)	Level 1: 60 min/week (30 min sessions) Level 2: 90 min/week (30 min sessions) Level 3: 120 min/week (40 min sessions)	Level 1: 150 min/week (50 min sessions) Level 2: 150 min/week (50 min sessions) Level 3: 180 min/week (60 min sessions)
Intensity	
 
Level 1: 55-60% of HR (at peak VO2 at baseline) Target RPE: 12-13
 
Level 2: 60-70% of baseline HR Target RPE: 13-14
 
Level 3: 70-85% of baseline HR for duration Target RPE: 14-16
 
	
 
Level 1: 50% of 1-rep max per weighted lifts (2 sets of 8-10 reps) Target RPE: 12-13
 
Level 2: 60% of 1-rep max per weighted lift (2 sets of 8-12 reps) Target RPE: 13-14
 
Level 3: 70% of 1-rep max per weighted lift for (2 sets of 10-14 reps) Target RPE: 14-16
 
	
When the second exercise regimen is added, begin at Level 1 in that regimen while continuing at the same level for the exercise regimen already underway.
 
Sessions will include 20-40 mins of AE and 2 sets of 8-14 reps, with intensities varying based on participant progress

*Example aerobic exercises:* March in place, jumping jacks, glute kicks, high knees, lateral shuffles, standing oblique crunch, speed skaters, mountain climbers

*Example resistance exercises:* Weighted lifts and weight bearing functional tasks for large muscle groups; seated knee extensions, standing hip abduction, standing hip extension, triceps extension, and shoulder abduction

---

Times do not include 10 min warm-up/cooldown per session (i.e. 20 mins total per wee k in Level 1 resistance training, 30 mins total per week in all other circumstances).

The prescribed progression from Level 1 – 3 includes 3 weeks at Level 1, 3 weeks at Level 2, and the remaining 6 weeks at Level 3. However, participant exertion ratings will be measured after all exercise sessions. The ratings must be at 13 or lower to progress to the next level.

Prior to initiating any activity involving strength training, the following considerations should be made:

- Resolve any acute arm or shoulder problems secondary to breast cancer treatment before exercise training
- Reduce or avoid upper body exercise if exercise causes swelling or changes in arm/shoulder symptoms
- Women with lymphedema should wear a compression garment during exercise
- Be aware of risk for fracture if treated with hormonal therapy, dx of osteoporosis, or bony metastases
